###### **9.5.3.1.1.2 Serious Adverse Event Definition**

A TEAE, Baseline event or suspected adverse reaction is considered serious if, in the view of either the Investigator or Sponsor, it results in any of the following:

- Death. This includes any death that occurs during the conduct of a clinical trial, including deaths that appear to be completely unrelated to the trial drug (e.g., car accidents).
- Life-threatening adverse experience. An AE or suspected adverse reaction is considered life-threatening if, in the view of either the Investigator or the Sponsor, its occurrence places the subject at immediate risk of death. It does not include an AE or suspected adverse reaction that, had it occurred in a more severe form, might have caused death.
- Persistent or significant disability or incapacity.
- Inpatient hospitalization or prolongation of an existing hospitalization.
- Congenital anomaly or birth defect.
- Other medically important event that, according to appropriate medical judgment, may require medical or surgical intervention to prevent one of the outcomes listed above.

Surgical procedures or other therapeutic interventions themselves are not AEs, but the condition for which the surgery/intervention is required is an AE and should be documented accordingly.

Elective surgeries that require hospitalization and treatment received at an emergency room or similar facility will not be considered as SAEs unless one of the definitions of an SAE listed above is met.

In addition, hospitalizations for planned procedures are not considered an AE, unless they are prolonged hospitalizations and emergency room visits <24 hours in duration are not considered hospitalizations.

[figure not shown]
#### **9.5.3.1.1.3 Non-serious Adverse Event Definition**

[figure not shown]
A non-serious AE includes any AE that is not described in the previous SAE category.

#### **9.5.3.1.1.4 Adverse Events of Special Interest**

An AESI is an AE (serious or non-serious) of scientific and medical concern specific to the Sponsor's product or program, for which ongoing monitoring and rapid communication by the Investigator to the Sponsor may be appropriate. Such events may require further investigation in order to characterize and understand them. AESIs may be added or removed during a trial by protocol amendment.

The following AESI is identified for this trial:

If any symptoms occur during the assessment in combination with the blood pressure reductions noted above, they are considered as part of the [REDACTED] event and will not be recorded separately as individual AEs.

If symptoms are reported by the subject throughout the assessment, without the blood pressure reductions noted above, then the symptoms will be recorded separately as AEs and [REDACTED] will not be recorded.

Signs and symptoms associated with [REDACTED] reported outside of the assessment will be captured as part of spontaneously reported AEs at each visit.

Depending on the timing, nature and severity of these spontaneous AEs, additional investigations will be conducted at the next scheduled visit or at an unscheduled visit, as clinically indicated per the Investigator's judgment. Whenever possible, the following data should be collected: concomitant medications, and blood pressure and heart rate measurements in supine and standing positions. Depending on the severity, plasma glucose level and ECG should be obtained per Investigator's clinical judgment.

#### **9.5.3.1.2 Documentation of Adverse Events**

AEs that are ongoing at the completion of HZNP-HZN-825-301 and/or occur prior to dosing on Day 1 will be considered pre-dose AEs. The TEAE reporting period begins with administration of the first dose of fipaxalparant (HZN-825) in this extension trial on Day 1 and continues until 4 weeks after the last dose of fipaxalparant (HZN-825) or premature discontinuation. All pre-dose AEs, TEAEs and AEs during the Follow-up Period must be recorded in the source documents and on the subject's eCRF. If a subject discontinues due to an SAE, that subject will be followed per Section [9.5.3.1.5](#).

If the Investigator observes an SAE after trial completion that he/she believes was possibly caused by fipaxalparant (HZN-825), the Investigator will report this SAE using the procedures described in Section [9.5.3.1.5](#). The Investigator is responsible for collecting and documenting the outcome of AEs/SAEs.

If specifically requested, the Investigator may need to provide additional follow-up information, such as discharge summaries, medical records, or extracts from the medical records. In this case, all subject identifiers, except for the subject number, will be blinded on the copies of the medical records before submission to the Sponsor.

Detailed information regarding all SAEs must also be recorded on the Serious Adverse Event Reporting Form. Whenever clinically appropriate, the Investigator should group together into a single term the signs and symptoms that constitute a single diagnosis. For example, cough, rhinitis and sneezing might be grouped together as “upper respiratory infection” if the Investigator is confident of the diagnosis.

#### **9.5.3.1.3 Intensity or Severity of Adverse Events**

All AEs, both serious and non-serious, will be assessed for severity using the Rheumatology Common Toxicity Criteria (RCTC) v2.0 [[Woodworth et al., 2007](#)]. The scale displays Grades 1 through 4 with unique clinical descriptions of severity for each AE (including abnormal laboratory values) based on this general guideline.

- Grade 1 (mild) – asymptomatic or transient, short duration (<1 week), no change in lifestyle, no medication or over-the-counter drugs
- Grade 2 (moderate) – symptomatic, duration 1 to 2 weeks, alter lifestyle occasionally, medications give relief (may be prescription), fipaxalparant (HZN-825) continued
- Grade 3 (severe) – prolonged symptoms, reversible, major functional impairment, prescription medications/partial relief, hospitalized <24 hours, temporary fipaxalparant (HZN-825) discontinuation or/and dose reduced
- Grade 4 (includes life-threatening) – at risk of death, substantial disability, especially if permanent, hospitalized >24 hours, permanent fipaxalparant (HZN-825) discontinuation

#### **9.5.3.1.4 Relationship or Causality to Fipaxalparant (HZN-825)**

The Investigator is obligated to assess the relationship between investigational product(s) and each occurrence of each AE and SAE.

Relatedness means that there are facts or reasons to support a relationship between investigational product and the event.

The Investigator will use clinical judgment to determine the relationship.

Alternative causes, such as underlying disease(s), concomitant therapy, and other risk factors, as well as the temporal relationship of the event to study treatment administration will be considered and investigated.

The Investigator will also consult the Investigator’s Brochure and/or product information, for marketed products, in their assessment.

For each AE/SAE, the Investigator must document in the medical notes that they have reviewed the AE/SAE and has provided an assessment of causality.

There may be situations in which a SAE has occurred and the Investigator has minimal information to include in the initial report. However, it is very important that the Investigator always assess causality for every event before the initial transmission of the SAE data.

The Investigator may change their opinion of causality in light of follow-up information and send a SAE follow-up report with the updated causality assessment.

The relationship of fipaxalparant (HZN-825) to each AE will be determined by the Investigator and the Sponsor based on the following definitions:

- Not related: There is no plausible temporal relationship or there is another explanation that unequivocally provides a more plausible explanation for the event.
- Related: There is evidence in favor of a causal relationship (i.e., there is a plausible time course) and at least one of the following criteria apply:
  - There is a reasonable pharmacological relationship (or known class effect).
  - There is no other more plausible explanation.
  - There is a positive de-challenge (without active treatment of the event).
  - There is a positive re-challenge.
  - There is a distinguishable dose effect.

#### **9.5.3.1.5 Reporting and Documenting Serious Adverse Events**

All SAEs beginning with the time of signing of the ICF and continuing through 4 weeks after the last dose of fipaxalparant (HZN-825) must be reported. The following steps will be taken to report promptly and document accurately any SAE, whether or not it appears to be related to fipaxalparant (HZN-825):

1. Report the SAE to the Sponsor by entering the information into the eCRF **immediately and not later than 24 hours** after becoming aware that a subject has experienced an SAE. If unable to access the eCRF, the event must be reported by submitting the completed SAE form **immediately and not later than 24 hours** after becoming aware that a subject has experienced an SAE.  
After the study is completed at a given site, the electronic data capture (EDC) system will be taken off-line to prevent the entry of new data or changes to existing data.  
If a site receives a report of a new SAE from a study subject or receives updated data on a previously reported SAE after the EDC system has been taken off-line, then the site can report this information on the paper-based SAE Form.

2. Perform appropriate diagnostic tests and therapeutic measures and submit all follow-up substantiating data, such as diagnostic test reports, hospital discharge summaries and autopsy report to the Sponsor's representative.
3. Conduct appropriate consultation and follow-up evaluation until the SAE outcome is known or the SAE is resolved. Outcomes for reported AEs/SAEs/AESIs are to be defined as follows:
  - Recovering/Resolving
  - Recovered/Resolved
  - Not Recovered/Not Resolved
  - Recovered/Resolved with sequelae
  - Fatal
  - Unknown
4. All new information for previously reported SAEs must be sent to the Sponsor immediately and no later than 24 hours after Investigator's awareness of the new information. If specifically requested, the Investigator may need to provide additional follow-up information, such as discharge summaries, medical records, or extracts from the medical records. Information provided about the SAE must be consistent with that recorded on the Adverse Events eCRF.  
There is no requirement to actively monitor study subjects after the study has ended with regards to study subjects treated by the Investigator. However, if the Investigator becomes aware of SAEs suspected to be related to investigational product, then these SAEs will be reported to the Sponsor immediately and no later than 24 hours after the Investigator's awareness of the event.  
Serious adverse events reported after the end of the study will be captured within the safety database as clinical study cases and handled accordingly based on relationship to investigational product.  
If further safety-related data is needed to fulfill any regulatory reporting requirements for a reportable event, then additional information may need to be collected from the subject's records after the subject ends the study.  
Review each SAE report and evaluate the relationship of the SAE to trial treatment.

#### **9.5.3.1.5.1 Monitoring of Serious Adverse Events Anticipated in the Trial Population**

SAEs are anticipated to occur in the trial population independent of the subject's exposure to fipaxalparant (HZN-825). These anticipated SAEs are provided in Section [17.13](#) (Serious Adverse Events Anticipated in the Trial Population) for reference. The list does NOT change the Investigator's reporting obligations or prevent the need to report an AE meeting the definition of an SAE, as detailed above. The purpose of this list is to alert the Investigator that some events reported as SAEs that are anticipated to occur in the trial population due to underlying disease may not require expedited reporting to the regulatory authorities in every country/region. The Sponsor will monitor these events throughout the course of the trial for any change in frequency.

### **9.5.3.1.6 Follow-up of Adverse Events**

The Investigator is obligated to follow-up any reported AE, SAE or AESI until all relevant clinical data are known to allow for an outcome or the event is resolved, in addition to confirming the causality assessment. Any ongoing trial drug-related AE present at the time of trial termination, including a clinically significant laboratory test abnormality, will be followed until resolved or until the event stabilizes and the overall clinical outcome has been ascertained.

The Investigator is obligated to perform or arrange for the conduct of supplemental measurements and/or evaluations as medically indicated or as requested by Sponsor to elucidate the nature and/or causality of the AE or SAE as fully as possible. This may include additional laboratory tests or investigations, histopathological examinations, or consultation with other healthcare professionals.

If a subject is permanently withdrawn from investigational product(s) and/or noninvestigational product(s)/auxiliary medicinal product(s) because of a SAE, this information must be submitted to Sponsor.

The Investigator will submit any updated SAE data to Sponsor immediately and no later than 24 hours of receipt of the information.

### **9.5.3.1.7 Medication Errors**

A medication error is any unintended failure in the drug treatment process, such as a mistake in the prescribing, dispensing, storing, preparation or administration of a medicine that leads to, or has the potential to lead to harm to the subject.

An overdose is defined as a known deliberate or accidental administration of investigational drug to a subject. For this trial, any dose of fipaxalparant (HZN-825) that is more than the dose that has been assigned will be considered an overdose.

An AE or SAE that is associated with a medication error, such as an overdose, is to be reported according to the procedures outlined in Sections [9.5.3.1.2](#) and [9.5.3.1.5](#), respectively. All medication errors or overdoses, with or without an AE or SAE, should be recorded as a protocol deviation and reported to the trial Medical Monitor in a timely manner. AEs or SAEs may not occur immediately after the medication error or overdose.

There is no clinical experience with overdose with fipaxalparant (HZN-825). No specific antidote or detoxification measures can be recommended to date. If accidental overdose is suspected, the subject should be treated symptomatically.

### **9.5.3.1.8 Review of Adverse Events and Emerging New Safety Information**

The Sponsor will perform an ongoing review of all AEs and all other emerging new information relevant to the safety of fipaxalparant (HZN-825), including periodic review and analyses of cumulative safety data for the trial.

### **9.5.3.1.9 Reporting of Investigational New Drug Safety Reports**

The Sponsor will report SAEs associated with fipaxalparant (HZN-825) to the appropriate regulatory authorities and all Investigators in accordance with the local and regional regulatory authorities laws and regulations.

### **9.5.3.1.10 Development Safety Update Reports**

The Sponsor will prepare and submit Development Safety Update Reports (DSUR) to all relevant regulatory authorities in countries and regions where the trial is conducted.

The Sponsor will prepare a single DSUR (also referred to as Annual Safety Report in the European Union [EU]) for the Sponsor Investigational Product. To ensure that consolidated safety information for the study is provided, this single DSUR will also include appropriate information on any other investigational products used in the clinical study, if applicable.

### **9.5.3.1.11 Regulatory Reporting Requirements for Safety Information**

If subject is permanently withdrawn from investigational product(s), and/or noninvestigational product(s)/auxiliary medicinal product(s) because of a SAE, this information must be submitted to the Sponsor.

Prompt notification by the Investigator to the Sponsor of SAEs is essential so that legal obligations and ethical responsibilities towards the safety of subjects and the safety of a study treatment under clinical investigation are met.

The Sponsor has a legal responsibility to notify both the local regulatory authority and other regulatory agencies about the safety of a study treatment under clinical investigation. The Sponsor will comply with country-specific regulatory requirements relating to safety reporting to the external review body and Investigators.

Individual safety reports for suspected unexpected serious adverse reactions will be reported by the Sponsor according to local regulatory requirements (e.g., electronic submission to the Eudravigilance database in the EU as per EU Clinical Trial Regulation 536/2014) as well as Sponsor policy and forwarded to Investigators as necessary.

An Investigator who receives an individual safety report describing a SAE or other specific safety information (e.g., summary or listing of SAEs) from the Sponsor will file it along with the Investigator's Brochure and will notify the external review body, if appropriate according to local requirements.

### **9.5.3.1.12 Safety Monitoring Plan**

Subject safety will be routinely monitored as defined in the Sponsor's safety surveillance and signal management processes.

### 9.5.3.2 Pregnancy and Lactation Reporting

Pregnancy testing will be performed for WOCBP. Serum pregnancy tests will be analyzed at a central trial laboratory and the urine pregnancy tests will be performed locally. In addition, urine pregnancy tests should also be done every 4 weeks after Day 1, which includes both in-clinic testing at scheduled visits prior to dosing [REDACTED] and at home ( $\pm 7$  day-window) by the subject and reported to the site [REDACTED]. A urine pregnancy test will also be done at the Safety Follow-up Visit (whether at the clinic or at a remote site).

If a female subject becomes pregnant during the Treatment Period, she should immediately notify the Investigator and fipaxalparant (HZN-825) should be permanently discontinued but the subject will be asked to continue in the trial for evaluations.

Pregnancy occurring in the partner of a male subject participating in the trial should be reported to the Investigator and the Sponsor immediately upon awareness of pregnancy. Monitoring of the subject's partner should continue until conclusion of the pregnancy.

Subjects should be instructed to continue contraception for 4 weeks after their last dose of fipaxalparant (HZN-825). Pregnancies occurring up to 4 weeks after the last dose of fipaxalparant (HZN-825) must also be reported to the Investigator.

Some examples of highly effective contraceptive methods that have a failure rate of <1% per year when used consistently and correctly are:

- Combined (estrogen- and progestogen-containing) hormonal contraception associated with inhibition of ovulation
  - Oral
  - Intravaginal
  - Transdermal
- Progestogen-only hormonal contraception associated with inhibition of ovulation
  - Oral
  - Injectable
  - Implantable
- Intrauterine device (IUD)
- Intrauterine hormone-releasing system (IUS)
- Bilateral tubal ligation
- Vasectomized partner
- Sexual abstinence from heterosexual intercourse

There are no expected drug interactions between fipaxalparant (HZN-825) and hormonal contraceptives.

Abstinence should only be used as a contraceptive method if it is in line with the subject's usual and preferred lifestyle. Periodic abstinence (calendar, symptothermal, postovulation methods) is not an acceptable method of contraception.

Details of all pregnancies and/or lactation in female subjects and pregnancies in female partners of male subjects will be collected after the start of study treatment and until 4 weeks after last dose of trial drug.

[figure not shown]
If a pregnancy is reported, the Investigator is to inform the Sponsor immediately and no later than 24 hours of learning of the pregnancy and/or lactation. The Investigator should report pregnancies to the Sponsor by submitting the completed pregnancy report form immediately and not later than 24 hours after becoming aware that the subject/subject's female partner has become pregnant (see Section 17.1 for contact information). The Investigator should counsel the subject and discuss the possible risks of continuing the pregnancy. If pregnancy continues and the subject signs the pregnancy consent form, monitoring should also continue to the conclusion of the pregnancy and the outcome of the pregnancy should be reported to the Sponsor.

Lactation information will be recorded on the Lactation Notification Form and submitted to Sponsor Global Patient Safety immediately and no later than 24 hours of the Investigator's awareness of the event.

#### **9.5.3.3 Vital Signs and Weight**

Blood pressure and pulse measurements will be obtained with the subject's arm unconstrained by clothing or other material and while the subject is sitting up. When possible, the same arm will be used for measurements for all trial visits.

Weight will be measured. To limit the potential for variability in weight collection, the subject should wear lightweight clothing and no shoes during weighing.

#### **9.5.3.5 Physical Examination**

A complete physical examination, including but not limited to cardiac, pulmonary, neurologic and skin assessments, as well as directed rheumatology assessments [REDACTED], [REDACTED], will be performed.

### **9.5.3.6 ECG**

ECG results will be recorded as normal or abnormal on the eCRF and all abnormal results will be evaluated by the Investigator as clinically significant or not clinically significant. Any clinically significant abnormal ECG, including a QT interval corrected for heart rate (QTc) >450 ms, should be confirmed by a repeat resting ECG at the same visit. The site personnel should ensure that ECGs are collected after the subject is supine for at least 10 minutes.

A copy of the ECG tracing will remain with the source documents.

### **9.5.3.7 Echocardiogram**

A standard transthoracic echocardiogram will be conducted on Day 1. However, an echocardiogram that has been performed during HZNP-HZN-825-301 and within the 3 months prior to HZNP-HZN-825-302 Day 1 can serve as the Trial Baseline echocardiogram if the subject has been clinically stable.

Additional echocardiograms will be conducted, if clinically indicated.

Echocardiogram results will be recorded on the eCRF as normal or abnormal and all abnormal results will be evaluated by the Investigator as clinically significant or not clinically significant. A copy of the echocardiogram results will remain with the source documents.

### **9.5.3.8 Laboratory Tests for Evaluation**

A central trial laboratory will be used for all protocol-specified laboratory evaluations, with the exception of urine pregnancy tests that will be performed locally at each site or at-home, as applicable, in order to maintain monthly pregnancy testing.

Chemistry parameters to be evaluated include total protein, albumin, sodium, glucose, phosphate, potassium, calcium, chloride, bicarbonate, blood urea nitrogen, creatinine, creatine kinase, uric acid, lactate dehydrogenase and liver function tests (ALT, AST, gamma glutamyltransferase, alkaline phosphatase, total bile acid, TBL, conjugated and unconjugated bilirubin, if applicable).

Lipid profile (total cholesterol, high-density lipoprotein cholesterol, low-density lipoprotein cholesterol, triglycerides) will also be evaluated.

Subjects should be fasting for the Day 1, Week 28 and Week 52/Premature Discontinuation Visits.

Hematology parameters to be evaluated include hemoglobin, hematocrit, red blood cell count (with morphology if blood cell count is abnormal), mean corpuscular volume (MCV), mean corpuscular hemoglobin (MCH), mean corpuscular hemoglobin concentration (MCHC), red blood cell distribution width (RDW), reticulocyte count, white blood cell count with differential (neutrophils, eosinophils, basophils, monocytes, lymphocytes) and platelet count.

Urinalysis parameters, including reflex testing if abnormal on dipstick, to be evaluated include urine glucose, protein, bilirubin, urobilinogen, pH, blood, ketone, nitrite, leukocyte esterase, appearance, specific gravity and color.

Samples for high-sensitivity C-reactive protein (hsCRP), erythrocyte sedimentation rate (ESR) and autoantibodies (anti-centromere antibody, anti-RNA polymerase antibody, anti-topoisomerase 1 and anti-U1 small nuclear ribonucleoprotein) will also be collected.

Instructions for the collection, handling and analysis of clinical laboratory samples will be provided to the site prior to trial site initiation.

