2. On Day 1 (Baseline), subjects will receive the first dose of fipaxalparant (HZN-825) in this extension trial in the clinic. All Day 1 assessments should be performed before the first dose of trial drug is administered in the clinic.
3. Performed as part of the Week 52 Visit of HZNP-HZN-825-301; if applicable, the result will be considered a Trial Baseline value for this extension trial.
4. Except when strictly unavoidable, the same person should perform the assessment at each evaluation during the trial. The mRSS assessment should be performed by a qualified Investigator (or designee).
5. The lung HRCT scan should be performed within ±2 weeks of the Week 52/PD Visit.
6. DLCO can be assessed within ±2-weeks of the Week 28 and Week 52/PD Visits.
7. Daily electronic diaries will be completed for 4 weeks starting on Day 1, 4 weeks starting at the Week 22 Visit and 4 weeks starting at the Week 46 Visit.
8. Perform for WOCBP. Serum pregnancy test at [REDACTED] (or as needed). Urine pregnancy tests should also be done every 4 weeks after Day 1, which includes both in-clinic testing at scheduled visits prior to dosing [REDACTED] and at home (also a ±7-day window) by the subject and reported to the site [REDACTED]. A urine pregnancy test will also be done at the Safety Follow-up Visit.
9. A complete physical examination, including but not limited to cardiac, pulmonary, neurologic and skin assessments, as well as directed rheumatology assessments [REDACTED]
10. Vital signs (blood pressure, heart rate, respiratory rate, temperature) will be measured at each visit.
11. Additional electrocardiograms or echocardiograms will be conducted, if clinically indicated. A standard transthoracic echocardiogram will be conducted on Day 1. However, an echocardiogram that has been performed during HZNP-HZN-825-301 and within the 3 months prior to HZNP-HZN-825-302 Day 1 can serve as the Trial Baseline echocardiogram if the subject has been clinically stable.
12. See Section 9.5.3.8 for details.
13. ESR must be processed within 1 hour of the blood draw.

14. Autoantibodies include anti-centromere antibody, anti-RNA polymerase antibody, anti-topoisomerase 1 and anti-U1 small nuclear ribonucleoprotein.
15. PK samples will be collected at each of the following visits: Day 1 (pre-dose), Week 4 (pre-dose and 2 to 4 hours post-dose) and Weeks 16, 28 and 40 (pre-dose). Note: all pre-dose samples will be collected prior to any fipaxalparant (HZN-825) administration for the day.

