#### **9.4.6 Trial Drug Administration and Timing of Dose for Each Subject**

Subjects will take 2 tablets of fipaxalparant (HZN-825) orally in the morning and evening with a meal. In the event a subject misses a dose, the dose should be taken along with the next planned dose (evening or morning) with a meal such that 4 tablets (600 mg) in total will be taken. Due to a less than dose-proportional increase in fipaxalparant (HZN-825) systemic exposure, the 600 mg dose taken in the event of a prior missed dose will be considered part of the planned dosing for this trial.

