## **9.5.2 Pharmacokinetic Measurements**

Blood samples will be collected from all subjects to evaluate the PK of fipaxalparant (HZN-825) at each of the following visits: Day 1 (pre-dose), Week 4 (pre-dose and 2 to 4 hours post-dose) and Weeks 16, 28 and 40 (pre-dose only at these 3 visits). For the Week 4 Visit (the only visit with post-dose PK samples), the morning dose regimen will be taken in the clinic. All pre-dose samples will be collected prior to any fipaxalparant (HZN-825) administration for the day. PK sample collection time and the most recent dosing time prior to PK sample collection will be recorded for all PK samples.

If the clinic visit is in the morning, on days when a pre-dose PK sample will be collected (i.e., Day 1 and Weeks 4, 16, 28 and 40), subjects will be instructed to withhold taking fipaxalparant (HZN-825) before the visit, and fipaxalparant (HZN-825) and a meal will be administered in the clinic after the pre-dose PK samples are taken. Time of fipaxalparant (HZN-825) administration in the clinic as well as the most recent dosing time prior to the visit will be recorded; 1 additional PK sample will be collected 2 to 4 hours after dosing in the clinic for during the Week 4 Visit.

If the clinic visit is in the afternoon, on days when a pre-dose PK sample will be collected (i.e., Day 1 and Weeks 4, 16, 28 and 40), subjects will be instructed to take fipaxalparant (HZN-825) before 8 a.m. with a meal and record dosing time; 1 PK sample will be

collected anytime during the clinic. For the Week 4 Visit, subjects will receive the evening dose during the visit (dosing time to be recorded) if it is at least 8 hours from the morning dosing and an additional PK sample will be collected 2 to 4 hours post-dose during this visit. At Weeks 16, 28 and 40, subjects will be instructed to take the evening dose at regular dosing time.

Instructions for collection, processing, handling, storing and shipping of PK samples will be detailed in a laboratory manual that will be provided to each site prior to site initiation.

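### For an afternoon Week 28 visit the protocol asks for fasting bloods but also tells subjects to take drug with a meal before 8 a.m., so Week 28 lipids can mix fed and fasted samples (minor)

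*Protocol*

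**What the plan says.** Protocol 9.5.3.8 lists a lipid profile (total, HDL and LDL cholesterol, triglycerides) and states: "Subjects should be fasting for the Day 1, Week 28 and Week 52/Premature Discontinuation Visits". The Schedule of Assessments (Protocol 2.1) places lipids at exactly those three visits. No number of fasting hours is given.

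Protocol 9.5.2 makes Day 1 and Weeks 4, 16, 28 and 40 pre-dose PK days and sets two branches by time of visit:

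- Morning visit: the subject withholds drug, and "fipaxalparant (HZN-825) and a meal will be administered in the clinic after the pre-dose PK samples are taken".
- Afternoon visit: "subjects will be instructed to take fipaxalparant (HZN-825) before 8 a.m. with a meal and record dosing time". One PK sample is then taken at any time during the visit.

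Protocol 9.5.3.8 also says: "Instructions for the collection, handling and analysis of clinical laboratory samples will be provided to the site prior to trial site initiation".

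SAP 10.3.3.1 summarises laboratory values and changes from baseline by visit and treatment group, with shift tables from baseline to each visit. It does not mention fasting status. It plans no formal testing of laboratory data.

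**The concern.** At Week 28 both instructions are current text and both can apply to the same subject on the same day. A subject with an afternoon appointment who follows 9.5.2 eats breakfast. A subject with a morning appointment comes in before dose and meal. Neither section refers to the other or says which gives way.

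Triglycerides respond to recent food. If fed afternoon samples and fasted morning samples go into one Week 28 column, a meal effect can look like a change from baseline or a grade shift, or can hide one. Only one other post-baseline lipid visit exists against which to check such a finding.

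**Working it through.** The documents give no figure to reproduce. The check sets the sections side by side and then uses clock arithmetic.

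**Step 1. Which visits carry which instruction** (Protocol 2.1, 9.5.2, 9.5.3.8)

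| Visit | Lipids drawn | Fasting asked for | PK-day dosing rule in 9.5.2 |
|---|---|---|---|
| Day 1 | yes, from the parent trial's Week 52 visit | yes | yes |
| Week 28 | yes | yes | yes |
| Week 52/PD | yes | yes | no |

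Of the 2 post-baseline lipid visits, 1 (Week 28) carries the conflicting afternoon meal instruction.

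**Step 2. Hours without food at an afternoon Week 28 draw**

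Hours = draw time minus meal time. The latest permitted meal is just before 08:00 (9.5.2). The 06:00 meal and all draw times are assumptions.

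| Meal with dose | Draw 12:00 | Draw 14:00 | Draw 16:00 | Draw 17:00 |
|---|---|---|---|---|
| 06:00 | 6 h | 8 h | 10 h | 11 h |
| 08:00 | 4 h | 6 h | 8 h | 9 h |

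For draws from 12:00 to 16:00 the range is 4 to 10 hours.

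**Step 3. When both instructions can be met**

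Earliest draw = meal time + fasting duration. The durations are assumed, because the protocol states none.

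- 8-hour fast: 06:00 + 8 h = 14:00; 08:00 + 8 h = 16:00.
- 12-hour fast: 06:00 + 12 h = 18:00; 08:00 + 12 h = 20:00.

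Under 8 hours, some later afternoon draws comply. Under 12 hours, no draw up to 17:00 does.

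**Step 4. Glucose**

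Post-baseline chemistry is drawn at Weeks 4, 10, 16, 22, 28, 40, 52/PD and the Safety Follow-up Visit, 8 visits in all. Fasting is asked for at 2 of the 8, so glucose is mostly non-fasting by design.

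**Step 5. Effect of visit time on the Week 28 PK sample**

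SAP 11 counts a sample as pre-dose only if it is taken 10 to 14 hours after the most recent dose. In the afternoon branch the hours in Step 2 are also hours since that morning's dose. Only the 06:00 dose with a 16:00 or 17:00 draw (10 or 11 hours) falls in the window. In the morning branch, with an assumed evening dose at 18:00 to 20:00, an 08:00 draw is 12 to 14 hours post-dose and a 10:00 draw is 14 to 16 hours. An early morning draw suits the window; a late morning draw may not.

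**The case against.** The strongest reply is that the clash is conditional. It arises only for an afternoon visit, and a site can obey both sections by booking Week 28 in the morning. That is right, and it is why the remedy is small. But 9.5.2 provides for afternoon visits and nothing steers Week 28 away from them. Protocol 9.5.1.1 asks that spirometry, also due at Week 28, be attempted at about the same time of day as in the parent trial, so a subject seen in the afternoon there has a reason to stay in the afternoon.

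A second reply is that fasting is undefined, so a late enough draw satisfies both rules. This also stands. The claim is that samples can mix, and it would be wrong to say that the two instructions can never both be followed.

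A third reply is that the site laboratory instructions may define fasting, fix the draw time or capture time of last food. They may; they are not available here. Even so, 9.5.2 would still tell the afternoon subject to eat.

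Three wider readings might be inferred, and the documents do not support them:

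- **Week 52/PD.** The general rule is "Subjects will take 2 tablets of fipaxalparant (HZN-825) orally in the morning and evening with a meal", with no exemption for this visit. But Week 52/PD is not a PK day and has no before-8 a.m. instruction. The request to attend fasting itself holds the meal, and so the with-meal dose, until after the draw. There is no conflict.
- **Glucose.** Step 4 shows that glucose is largely non-fasting by design, so one more fed sample matters little.
- **Day 1.** The afternoon rule names Day 1 too, but those bloods are "Performed as part of the Week 52 Visit of HZNP-HZN-825-301". Whether they were fasted depends on the parent protocol, which is not available here.

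**Conclusion.** The inconsistency is real and confined to lipids, mainly triglycerides, at afternoon Week 28 visits. One of the two post-baseline lipid visits is affected. Any subject whose draw comes too soon after the instructed breakfast gives a fed sample, and the SAP tables would not distinguish it from a fasted one.

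The severity is minor. The affected output is descriptive safety tables with no planned testing, and the FVC endpoint is untouched. The share of afternoon visits is not stated and cannot be estimated from the documents, so no affected percentage is offered. The size of any mixing also rests on an unstated fasting duration, on the assumed meal and draw times above, and on laboratory instructions not seen.

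**What to change.** **Protocol 9.5.2 and 9.5.3.8.** Schedule the Week 28 bloods in the morning before dose and meal, using the existing morning branch of 9.5.2, and state the fasting duration. An early draw also suits the 10 to 14 hour pre-dose PK window.

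**Data collection.** Record time of last food with the lipid sample, if the laboratory form does not already do so.

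**SAP 10.3.3.1.** Flag Week 28 lipid samples that do not meet the stated fasting duration.

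**Data already collected.** Protocol 9.5.2 provides that "PK sample collection time and the most recent dosing time prior to PK sample collection will be recorded for all PK samples". Flag by the hours between the recorded with-meal dose and the sample, using the lipid collection time where it is held, since it need not equal the PK time. Do not flag every same-morning dose: a 06:00 dose with a 15:00 draw is 9 hours apart and would pass an 8-hour rule. The interval is only a proxy. It assumes that the dose was taken with food as instructed and that nothing was eaten afterwards.

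**What not to do.** Holding dose and meal until after an afternoon draw is a poor substitute. With an assumed evening dose at 18:00 to 20:00, a 12:00 to 16:00 draw falls 16 to 22 hours post-dose, outside the PK window. Keeping the spacing used at Week 4 ("if it is at least 8 hours from the morning dosing") would then put the evening dose at 20:00 to 24:00.

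**Cost.** Scheduling is less flexible at one visit, and there may be tension with same-time-of-day spirometry. The wording change would have to go into a formal amendment with IRB/IEC approval (Protocol 9.7), at up to 135 sites, so it is best carried with other changes. The SAP change is one sentence.
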